1.0 Introduction

1.1 Study synopsis

Trial	Parallel randomised controlled trial
Phase	Proof-of-concept
Sample size	60
Study population	Otherwise healthy men and postmenopausal women aged 18-70 with signs of prediabetes, but not clinically diagnosed with diabetes.
Duration	24 weeks
Background	Pre-diabetes is characterised by high blood glucose levels, high plasma cholesterol, low-density lipoprotein (LDL) and high-density lipoprotein (HDL). Dietary fibre consumption has been hypothesised to improve these metabolic parameters through microbial fermentation and the subsequent production of short-chain fatty acids (SCFAs).
Objectives and aims	This trial will investigate whether a powdered fibre mix (myota Metabolic Regulator) helps maintain healthy blood glucose levels in participants with prediabetes, where high blood sugar is a risk of diabetes.
Recruitment strategy	Participants will be identified through the Lindus Health Primary Care Network, and social media advertising may also be used. Participants will complete online pre-screening, trial registration and informed consent. Eligibility will be confirmed by the Research Nurse during a video call with the participant.
Randomisation	Participants will be randomised to Placebo or the Myota Metabolic Regulator (powdered fibre mix) with a 1:1 randomisation ratio stratified by gender and BMI.
Intervention	The functional food, Myota Metabolic Regulator, consisting of 20g of a powdered fibre mix, to be taken daily alongside usual diet for 24 weeks.
Comparator Group	Placebo will be 2g of powdered cellulose, to be taken daily alongside usual diet for 24 weeks.
	Participants will be asked to attend an appointment (~2.5-3 hours) at a central clinic in London at baseline, week 16 and week 24. During the appointment, a nurse will obtain blood samples for biomarker measurements (see Outcomes for full list), ask the participant to complete an OGTT (baseline and week 16 only) and collect blood pressure recordings. In addition, participant surveys will collect any (Serious) Adverse Events at the end of weeks 4 and 8 and then monthly, usability testing at 16 and 24 weeks, and intervention adherence on a daily basis for 24 weeks. The Lindus Health Research Nurse will contact participants throughout the trial.

1.2 Background and rationale

1.2.1 Background

It is well understood that dietary fibre contributes to a healthy metabolism and maintenance of insulin sensitivity (1). In addition to the more mechanical benefits of fibre, it is fermented by the gut microbiome to produce Short Chain Fatty Acids (SCFAs) which promote healthy metabolic processes (2).

High-throughput multi-omic technologies, genomics, metabolomics and microbiome analyses, are increasingly sensitive and cost-effective tools for gaining mechanistic insights into human health. A particularly fertile terrain for developing novel clinical interventions lies in the human gut microbiota, the composition of which has been associated with a growing number of clinical indications including pre-diabetes. This complex community spans enormous biochemical space to scavenge otherwise indigestible nutrients and other chemicals present in our diet, processing them into substances that can play critical roles in human physiology. It is therefore one of the goals of 21st Century healthcare to design therapies that target and exploit the microbiota and its metabolic output, with particular emphasis on gut diseases such as pre-diabetes which may progress to Type 2 Diabetes and result in significant economic and public health costs.

A critical component to achieving this goal in the context of pre-diabetes is gaining control over microbial fermentation of dietary fibre in the colon, which typically involves the production of the Short Chain Fatty Acids (SCFAs) (2,3). Colonic SCFAs (acetate, propionate and butyrate) have a number of physiological functions, and as such lie at the heart of the symbiotic relationship between host and microbe. It has long been known that microbial butyrate serves as the dominant energy source for colonocytes (4). More importantly in the context of pre-diabetes, butyrate promotes intestinal gluconeogenesis, with beneficial impacts to insulin sensitivity and metabolic status (3). This explains why deficiencies in butyrate production have been associated with Type-2 diabetes and insulin resistance.

This understanding of SCFAs provides us with a more complete picture of the main mechanisms by which dietary fibres act on our metabolism to promote insulin sensitivity to maintain healthy blood glucose in individuals with pre-diabetes and/or Type-2 diabetes (1,5). The first mechanism involves mechanical benefits of more viscous fibres (e.g. arabinoxylan), which reduce post-prandial glucose uptake from a given meal if ingested with the fibre. The second mechanism involves the action of SCFAs on intestinal gluconeogenesis. Finally, it is also understood that SCFAs exert anti-inflammatory pressure on the host's immune system, which is also in line with preventing and/or reversing the pre-diabetic state. These mechanisms are complementary and non-overlapping.

1.2.2 Rationale

The question then arises: can we increase fibre intake to improve SCFA production? Several studies have tested the effect of dietary fibre on plasma SCFA levels, and have shown statistically significant increases in plasma and faecal SCFAs following fibre consumption (6,7,8,9). However, we now know from our research at Myota that different individuals can

sometimes have radically different fermentation capabilities depending on their gut microbiome composition (10). What this means is that when different individuals are fed the same dietary fibre (e.g. inulin) in the same quantity, their microbiomes produce different quantities of SCFAs. These differences in fermentation capability reflect the fact that each individual has a distinct microbiome. They also explain the fact that clinical improvements associated with boosting SCFA production through fibre are significantly diluted by the fact that certain individuals in the respective cohorts may be unable to produce significant quantities of butyrate from the fibre in question. Put differently, we will not observe the full potential efficacy of fibre supplementation unless we account for the fact that different individuals would respond better to different individual fibres as a function of their fermentation capability.

Myota has extensively studied the fermentation capabilities across individuals, and in so doing constructed a database of over 80 volunteers whose fermentation capabilities were analysed experimentally in great detail. This has allowed an understanding of the inter-individual variability in SCFA production from particular fibres, which in turn enabled the calculation of mixtures of fibres that result in the most SCFA (and particularly butyrate) production on average across individuals. Thus, Myota has leveraged cutting edge science in the field of microbiome and nutrition to create a fibre mix which: firstly, includes the relevant quantities of the right fibres in order to obtain the acute (post-prandial) glycaemic benefits of consuming fibre; secondly, uses Myota's proprietary database to compute mixes that promote SCFA production across different individuals with varying microbiome compositions.

In this study, we aim to demonstrate the efficacy of a fibre mix as a functional food in improving clinical biomarkers for people identified as having pre-diabetes, i.e. glycaemic responses (HbA1c, oral glucose tolerance, and fasting blood glucose). Participants will be randomised to either intervention (20g of precision fibre mix daily alongside usual diet) or control (Placebo).

1.3 Study Objectives

1.3.1 Primary Objective

Primary Objective	Outcome Measure	Timepoint(s) of evaluation of this outcome measure
To compare the effect of Myota's Metabolic Regulator versus placebo on HbA1c levels	Relative change in HbA1c from baseline to 16 weeks	Baseline and 16 weeks

1.3.2 Secondary Objectives

Secondary Objective	Outcome Measure	Timepoint(s) of evaluation of this outcome measure
To compare the effect of the Myota Metabolic Regulator versus placebo on:		

HbA1c	Change in HbA1c	Baseline, 16 and 24 weeks
Insulin	Change in Insulin	Baseline, 16 and 24 weeks
Insulin sensitivity	Insulin sensitivity, measured using ISI-OGTT	Baseline and 16 weeks
Lipid profile	Cholesterol [total, LDL, HDL] and triglycerides)	Baseline, 16 and 24 weeks
Inflammatory markers	IL-6, IL-8, IL-10, CRP, TNF-a	Baseline, 16 and 24 weeks
Blood pressure	Diastolic and systolic blood pressure	Baseline, 16 and 24 weeks
To investigate the safety of the Myota Metabolic Regulator	Evaluation of overall safety of the Myota Metabolic Regulator by the monitoring of: • Number of AEs • Number of SAEs	Continuously for the duration of taking the intervention/placebo
To investigate intervention adherence	Intervention adherence questionnaire	Daily for the duration of the intervention, 24 weeks
To investigate usability	Usability questionnaire	At 16 and 24 weeks

2.0 Study Methods

2.1 Trial design

This trial is a two-arm, individually randomized, single-blind placebo-controlled trial. The total trial duration is 24 weeks. Participants will be assigned to the intervention or placebo for 24 weeks. Primary and secondary outcomes will be assessed at baseline, 16, and 24 weeks (*Section 1.3*).

2.2 Randomisation

Consenting participants who have met all of the eligibility criteria and completed the baseline assessment will be individually randomised into one of the two groups, using a web based system (Sealed Envelope), at a ratio of 1:1, stratified by gender and BMI.

2.3 Sample size

This study aims to recruit 60 participants, men and post-menopausal women aged 18-70 diagnosed with pre-diabetes, but not receiving treatment for type 2 diabetes. As this is a pilot study, our sample size has not been derived statistically, but informed based on previous studies assessing fibre-based interventions in pre-diabetes cohorts. Our sample size is therefore consistent with previous studies assessing fibre-based interventions in similar populations. Results from previous studies (Zhou et al. 2018, n = 43; Peterson et al., 2018, n = 68) suggest that 60 participants is an adequate sample size to capture meaningful differences in our primary and secondary outcome measures. A sample size of 30 in each arm results in a power of 80% to detect effects of at least d = 0.74.

2.4 Statistical interim analyses and stopping guidance

One interim analysis will be conducted after 16 weeks of follow-up. Those involved in the day to day conduct of the trial will remain blinded to the outcome of the analysis.

3.0 Statistical Principles

3.1 Confidence intervals and P values

Effects will be considered statistically significant if the associated *p*-value is smaller than 0.05.

3.2 Adherence and protocol deviations

Adherence will be reported as a percentage of total intervention days during which participants reported taking the intervention / placebo. This will be assessed by participants completing a daily online survey recording whether they have consumed the full sachet of intervention/placebo. A significant deviation is defined as a participant who consumes the intervention less than 70% of the time.

3.3 Analysis populations

3.3.1 Intention to Treat (ITT)

All randomised study participants. This will be seen as the primary population for the analysis.

3.3.2 Per protocol (PP)

All randomised study participants who complete the trial without significant deviations from the protocol requirements. Analyses of this population is seen as a sensitivity analysis to investigate whether conclusions are sensitive to assumptions regarding the pattern of missing data.

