4.4 Withdrawal

Participants may choose to stop the intervention but may remain on study follow-up. If the participant withdraws completely, all recorded data will be analysed. If the participant starts antidiabetic medications during the trial, they will be withdrawn from the trial as antidiabetic treatment is an exclusion criteria. They will continue to receive follow up surveys to ensure safety monitoring. In addition, the Investigator may discontinue the participation of a participant from the study at any time, if this is considered necessary for any reason including, but not limited to:

- Ineligibility
- Clinical decision for other reasons

The type of withdrawal and reason for withdrawal will be recorded.

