5.2.2 Primary Outcome

A two-tailed t-test will be used to compare the percent change in HbA1c levels from baseline to 16 weeks between treatment and placebo.

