5.5 Sensitivity analyses

As a sensitivity analysis, the primary and secondary outcomes will be analyzed using the PP population to investigate whether conclusions are sensitive to assumptions regarding the pattern of missing data.

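### The per-protocol set for the 16-week outcomes is defined by 24-week completion and intake, so events after the outcome is measured can decide who is in it

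*SAP*

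**What the plan says.** Section 3.3.2 limits the PP set to "All randomised study participants who complete the trial without significant deviations from the protocol requirements". Section 2.1 gives the length of the trial: "The total trial duration is 24 weeks".

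Section 3.2 supplies the deviation rule: "A significant deviation is defined as a participant who consumes the intervention less than 70% of the time". That sentence names no time window. The reporting sentence in the same section does: "Adherence will be reported as a percentage of total intervention days during which participants reported taking the intervention / placebo". Section 1.3.2 lists the adherence questionnaire as "Daily for the duration of the intervention, 24 weeks".

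Section 5.5 states that "the primary and secondary outcomes will be analyzed using the PP population". The primary analysis in section 5.2.2 is a t-test to "compare the percent change in HbA1c levels from baseline to 16 weeks between treatment and placebo". Section 5.2.3 adds a t-test of insulin sensitivity over the same 16 weeks.

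Under section 4.4, participants may stop the product and stay in follow-up. Of those who start antidiabetic medication at any time in the trial, it says "they will be withdrawn from the trial". No section gives a completion or intake rule that stops at week 16.

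**The concern.** Whether a participant followed the plan up to a week-16 measurement is settled by week 16. Under the definition as written, membership of the PP set for that measurement is settled only at week 24. Two things follow.

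- **Observed values are discarded for later reasons.** A participant who took the product as planned, gave a week-16 sample and left in week 20 has contributed everything the primary comparison needs, yet is excluded from its PP analysis.
- **Exposure before the measurement can be misclassified in both directions.** Intake in weeks 17–24 can remove someone who was adherent when HbA1c was measured, or admit someone who was not.

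Sections 3.3.2 and 5.5 present the PP analysis as a check on sensitivity to missing-data assumptions, and it is the only sensitivity analysis in section 5.5. If it differs from the intention-to-treat (ITT) result at week 16, the cause could be the removal of people whose value was not missing at all. That removal may also be related to outcome: a start of antidiabetic medication in weeks 17–24 leads to withdrawal and is plausibly linked to glycaemia, which is the endpoint.

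**Working it through.** **The plan's own figure.** The only design figure is in section 2.3: 30 per arm, 80% power, d = 0.74. A two-sided t-test at 0.05 gives 80.5%, so it reproduces. The point below does not depend on it.

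**Inputs**

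- Trial and intervention: 24 weeks (section 2.1), so 24 × 7 = 168 days.
- Primary outcome and insulin sensitivity: week 16 (sections 5.1.1, 5.2.2, 5.2.3), so 16 × 7 = 112 days.
- Days after the outcome: 168 − 112 = 56.
- Adherence threshold: 70% (section 3.2).
- Denominator: 168 days, taken from the reporting sentence in section 3.2 because the deviation sentence gives none.

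**Completion rule (explicit).** PP requires completion, the trial is 24 weeks, and section 5.5 uses the one PP set for the primary outcome. Leaving on any day from 113 to 168 therefore removes a participant from the week-16 PP analysis, whatever their intake. No arithmetic is needed.

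**Intake rule (on the 168-day reading)**

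- Days needed over 24 weeks: 0.70 × 168 = 117.6, so 118 (118/168 = 70.2%).
- Days needed if counted to week 16: 0.70 × 112 = 78.4, so 79 (79/112 = 70.5%).

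| Intake to week 16 | Needed in the last 56 days | Consequence under the current rule |
|---|---|---|
| 112/112 (100%) | 118 − 112 = 6 | Excluded if none is taken afterwards: 112/168 = 66.7% |
| 79/112 (70.5%) | 118 − 79 = 39 | Excluded if fewer than 39 days are taken |
| 78/112 (69.6%) | 118 − 78 = 40 | Below 70% at week 16, but can be kept |
| 62/112 (55.4%) | 118 − 62 = 56 | Below 70% at week 16, but kept with full later intake |

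Thus everyone with 79 to 112 days by week 16 still depends on later intake, and anyone with 62 to 78 days can be brought in by it.

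**Possible size.** The SAP gives no late-exit rate. Assume 5% to 15% of the 60 leave in weeks 17–24, each with a week-16 HbA1c: 0.05 × 60 = 3 and 0.15 × 60 = 9 observed values dropped by the completion rule alone. If the loss is equal in both arms (28.5 or 25.5 per arm on average), power at d = 0.74 falls from 80.5% to 78.4% or 73.6%. The loss of precision is modest; the selection matters more.

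**After the change.** With a 16-week window, status is fixed by day 112. The 112/112 participant is included whatever follows, and the 62/112 participant is excluded whatever follows.

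**The case against.** The strongest reply has four parts.

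1. **The intake window is not fixed.** The deviation sentence names no denominator, so the 168-day figures rest on the neighbouring reporting sentence. This is correct, and those figures are conditional on that reading. It does not touch the completion rule, which is explicit and enough on its own. If the window is regarded as open, section 3.2 needs the same clarification.
2. **The stakes are small.** ITT is the primary population, no decision rule depends on PP, and this is a 60-person proof-of-concept trial. This stands and limits the severity. The intake patterns in the table are boundary cases, and nothing in the SAP shows that they are likely.
3. **Any PP set selects on behaviour after randomisation, and a 16-week set would still drop observed values for low intake.** This is also true. A PP comparison will not isolate missing-data assumptions even after the change. But intake before week 16 bears on the exposure behind the measured value, whereas events after week 16 do not. That part of the selection is avoidable.
4. **Week-16 HbA1c would appear in two PP sets**, one for the t-test and one for the repeated-measures model. This stands as a matter of presentation. A model that spans week 24 can reasonably use a 24-week set, provided the report states which set each analysis uses.

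The protocol, not seen here, might define completion by time point. The SAP nevertheless defines the set and states where it applies, and as written that definition is wrong for the 16-week outcomes.

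**Conclusion.** The concern holds. Followed as written, the SAP removes valid week-16 values from the PP analysis of the primary outcome, and from that of insulin sensitivity, because of events in weeks 17–24. The completion clause establishes this without any assumption. The intake effects (66.7% excluded despite perfect intake to week 16; 55.4% by week 16 kept) assume that the 70% is counted over 168 days.

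The number of participants affected cannot be derived; 3 to 9 of 60 is an illustration under assumed late-exit rates of 5% to 15%. The ITT primary result is unaffected. The correction should be made because it is cheap and concerns the only sensitivity analysis planned in section 5.5, but it does not threaten the trial's main conclusion.

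**What to change.** Amend sections 3.2 and 3.3.2 so that PP membership follows the time point of the outcome:

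- **For the two 16-week t-tests** (percent change in HbA1c, section 5.2.2; change in insulin sensitivity, section 5.2.3): a completed week-16 assessment, and the existing 70% threshold counted over days 1–112, that is at least 79 days. State that events after week 16 do not affect membership.
- **For the repeated-measures models in section 5.2.3 that include week 24**: the present set, with its denominator written out as trial completed and intake on at least 118 of 168 days.

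The threshold itself does not change, and neither do the withdrawal rules. The cost is two sentences. Adherence is already recorded daily, so no further data are needed. A 16-week set also has a practical advantage: membership is known for each participant at week 16, whereas 24-week status cannot be known at the section 2.4 interim analysis for anyone still in weeks 17–24, should a PP result be wanted there.

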4.0 Trial Population

4.1 Eligibility

Eligibility review will be conducted remotely by the Research Nurse during the telephone/video call with the participant. At the start of the call, the Research Nurse will reiterate the trial procedures and potential risks and benefits associated with taking part, as outlined in the PIS. Informed consent has already been provided online by the participant through signing the ICF, and the nurse will reaffirm consent with the participant during this call. Once reaffirmed, the Research Nurse will use medical history obtained from the participant to confirm whether they are eligible using the inclusion/exclusion criteria checklist. The participant's GP will be asked to confirm any inclusion/exclusion criteria where there is any uncertainty.

For all participants, GPs will be asked to confirm a HbA1c result of between 6.0% and 6.4% in the previous 12 months. A record of screen failures for those who do not meet the inclusion/exclusion criteria will be retained.

Once eligibility has been confirmed, the participant will be booked in to attend their first appointment where baseline measurements will be taken.

4.1.1 Inclusion Criteria

- Able and willing to provide informed consent
- Have a Body Mass Index (BMI) of at least 25 kg/m²
- Men or post menopausal women aged 18 70
- Identified as pre-diabetic (HbA1c 6.0% (42 mmol/mol) to 6.4% (47 mmol/mol)) within the previous 12 months
- Baseline HbA1c result within the range 5.8% (40 mmol/mol) 6.5% (48 mmol/mol)
- Willing to complete in clinic blood tests and a participant trial survey
- Have access to a smartphone or a computer

4.1.2 Exclusion Criteria

- Receiving medication to treat Type 1 or Type 2 diabetes in the previous 6 months
- Have a Body Mass Index (BMI) <25 kg/m² and >45 kg/m²
- Loss of more than 5% body weight in last 3 months
- Current participation in weight loss program or planned in the next 16 weeks
- Steroid use (except for over the counter NSAID's, topical steroids and inhalers)
- Severe hepatic diseases (including chronic persistent hepatitis, liver cirrhosis or the co-occurrence of positive hepatitis B virus surface antigen and abnormal hepatic transaminase (serum concentrations of alanine transaminase or aspartate transaminase >2.5× the upper normal limit))
- Continuous antibiotic use for >3 days within 4 weeks prior to enrolment
- Continuous use of weight-loss drug for within 3 months of study entry
- Gastrointestinal surgery (except for appendicitis or hernia surgery or co-existing pathology (Crohn's disease, celiac, endometriosis, prostate cancer))
- Severe mental illness within 6 months prior to enrolment
- Receiving drug therapy to treat cholecystitis, peptic ulcers, urinary tract infection, acute pyelonephritis, urocystitis or hyperthyreosis
- Pituitary dysfunction
- Severe organic diseases, including cancer, coronary heart disease, myocardial infarction or cerebral apoplexy
- Infectious diseases, including pulmonary tuberculosis and AIDS
- History of alcoholism or substance abuse
- Significant dyslipidaemia (>3 month use of low dose statins permitted*)
- Severe hypertension (>160/100)
- Using any food supplements for blood glucose control (e.g. chromium picolinate) within 2 months of trial entry

